8.3 Safety Assessments

Details regarding specific safety procedures/assessments to be performed in this study are provided.

Planned time points for all safety assessments are provided in the SoA.

8.3.1 Physical Examinations

Complete and directed physical examinations will be conducted during the visits outlined in the SoA (Section 1.3) by an investigator or medically qualified designee (consistent with local requirements) as per institutional standard.

Clinically significant abnormal findings during screening should be recorded as medical history.

Directed physical examination performed throughout the treatment period will at a minimum include assessment of the cardiovascular system and hemodialysis access site.

8.3.1.1 Height

Height will be measured without shoes using a stadiometer or other appropriate device at screening/Visit 1.

8.3.1.2 Weight

Body weight will be measured without shoes, jacket or coat removed, using a standardized scale at each time point specified in the SoA (Section 1.3) post-dialysis.

8.3.2 Systemic Infusion Reaction Assessment

Participants will be monitored for up to 1 hour after the administration of study intervention during the loading phase (first 3 treatment visits) as outlined in the SoA (Section 1.3). During this time, signs and symptoms of a systemic infusion reaction including, but not limited to, fever, vital sign changes (tachycardia/hypotension), pruritis, urticarial (hives), lip swelling, angioedema, bronchospasm, stridor, hoarseness, and shortness of breath will be monitored. Infusion reactions must be assessed, managed promptly, and reported as AEs.

Infusion Reaction Management

The risk of infusion reactions to MK-2060 is considered low since the molecule contains primarily human sequences; however, infusion reactions may be observed. Due to the expected low risk and since one of the objectives of the study is to characterize the safety profile of MK-2060, no prophylactic pre-medications to reduce the minimal risk of infusion reactions will be given prior to MK-2060 administration.

Participants who experience infusion or hypersensitivity reactions in conjunction with the infusion of study intervention should receive appropriate supportive care measures as deemed necessary by the treating physician. If a reaction occurs, participants should be carefully observed until complete resolution of all signs and symptoms. Report any AEs according to the guidelines in Section 8.4.

8.3.3 Vital Signs

Vital signs will be measured at each study visit before initiation of hemodialysis and administration of study intervention as outlined in the SoA (Section 1.3). Vital signs assessed will include body temperature, respiratory rate, heart rate, and BP. Participants should be resting in the semi-recumbent position for at least 10 minutes prior to having vital signs measurements obtained.

8.3.3.1 Body Temperature

Body temperature will be a single measurement. Temperature will be measured according to standard of practice.

8.3.3.2 Heart Rate and Blood Pressure

Heart rate and BP will be performed in triplicate measurements, obtained at least 1 to 2 minutes apart and before initiation of hemodialysis and administration of study intervention. The mean of these measurements will be recorded and used as the baseline to calculate change from baseline for safety evaluations (and for rechecks, if needed).

The correct size of the BP cuff and the correct positioning on the participant's limb is essential to increase the accuracy of BP measurements. Whenever possible, BP measurements should be obtained using the same arm or leg, same BP monitoring device, and same examiner at each visit.

8.3.4 Electrocardiograms

A standard supine 12-lead ECG will be obtained and reviewed by an investigator or medically qualified designee (consistent with local requirements) at the visits outlined in the SoA (Section 1.3). The ECG should be recorded with a paper speed of 25 mm/sec and equivalence of 1 mV signal to 10 mm vertical deflection in the ECG.

Clinically significant abnormal findings during the screening period should be recorded as medical history. Assessments may be repeated during the study, as clinically indicated.

- Participants should avoid the ingestion of caffeine and nicotine-containing products for at least 30 minutes before the scheduled ECGs.
- ECGs should be performed after the participant has rested quietly for at least 10 minutes in a supine position and before the assessment of blood pressure and heart rate as well as before blood collection.

All ECGs performed should be reviewed at the investigative site for participant safety monitoring. The investigator is responsible for retaining all copies of the ECG reports.

8.3.5 Clinical Safety Laboratory Assessments

- Refer to Appendix 2 for the list of clinical laboratory tests to be performed and to the SoA for the timing and frequency.
- The investigator or medically qualified designee (consistent with local requirements) must review the laboratory report, document this review, and record any clinically relevant changes occurring during the study in the AE section of the CRF. The laboratory reports must be filed with the source documents. Clinically significant abnormal laboratory findings are those which are not associated with the underlying disease, unless judged by the investigator to be more severe than expected for the participant's condition.
- All protocol-required laboratory assessments, as defined in Appendix 2, must be conducted in accordance with the laboratory manual and the SoA.
- If laboratory values from nonprotocol-specified laboratory assessments performed at the institution's local laboratory require a change in study participant management or are considered clinically significant by the investigator (eg, SAE or AE or dose modification), then the results must be recorded in the appropriate CRF (eg, SLAB).
- For any laboratory tests with values considered clinically significantly abnormal during participation in the study or within 90-days after the last dose of study intervention, every attempt should be made to perform repeat assessments until the values return to normal or baseline or if a new baseline is established as determined by the investigator.

8.3.5.1 Serum Pregnancy Test

All WOCBP (see Section 10.5.1 for definition) participating in the study will have a serum pregnancy test at visits indicated in the SoA and when pregnancy is suspected. Participants with a positive pregnancy test must be discontinued from study treatment and followed (Section 7.1).

61

Germany-specific requirements are in Appendix 7.

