Weight	X	X			X	X	X	X	X	X	X	X	X	X	X	X	Post-dialysis
Directed Physical Examination		X				X	X		X	X							
Vital Signs	X	X	X	X	X	X	X	X	X	X	X	X	X	X	X	X	Pre-dialysis. BP and HR to be measured in triplicate.
12-lead ECG	X										X		X			X	
Clinical Events Assessment		X	X	X	X	X	X	X	X	X	X	X	X	X	X	X	Collection of events for selected endpoints
Vital Status Assessment			Х	X	X	X	X	X	X	X	X	Х	X	X	X	X	Assessed whenever participant's vital status is in question.
AE/SAE Review	Х	X	X	X	X	X	X	X	X	X	X	X	X	X	X	X	Participants should be trained to contact the site to report AEs as soon as they occur
KDQOL-SF & EQ- 5D-5L Questionnaires		X								X	X		X				At preselected sites every 6 months
Central Laboratory	Assessn	ents										_					
Serum FSH – (WOCBP only)	X	X ^b															To confirm postmenopausal status.
Pregnancy test (Serum) in WOCBP	Xc						X	X	X	X			X				Germany-specific requirements are in Appendix 7

Study Period	Scree	ening					Т	reatme	nt Perio	od			Prematur	e Interventio	n Discontir	nuation	Notes
Visit Number/Title	1 Screen	2 Rand	3	4	5	6	7	8	9	Visit n	Final Efficacy Visit	Safety Follow-up Visit	Premature Discon. Visit	Safety Follow-up Visit	Visit n	Final Efficacy Visit	
Scheduled Days/Month	Day -30 to Day 1	Day 1	Day 3	Day 5	Day 8	Day 15	Day 29	Day 57	Day 85	Every 3 months	Based on Efficacy Cutoff date ^a	3 months after Final Efficacy Visit	Study Intervention Discon.	3 months after Discon.	Every 3 months	Based on Efficacy Cutoff date ^a	
Visit Window			±1 day	±1 day	±1 day	±3 days	±3 days	±5 days	±7 days	±7 days		±7 days	±7 days	±7 days	±7 days		Refer to Section 6.4.
Coagulation (INR, PT, aPTT)	X																To be collected separate from hematology laboratory tests
Hematology	X	X	X	X	X	X	X	X	X	X	X		X			X	
Liver Function Tests		X			X	X	X	X	X	X	X		X			X	
Chemistry		X			X	X	X	X	X	X	X		X			X	
Pharmacokinetics/In	mmunog	enicity	/Pharn	nacody	namic	s/ Bion	arkers	5									
Blood for PK evaluation		X ^d			Xe	Xe	Xe		X ^d	Xe	Xe		X ^e				Record date and time of collection. To be collected for all participants in main study.
Blood for ADA		X					X		X	X	X		X				Collect pre-dialysis
Blood for PT/aPTT/FXI Activity		X			X	X	X	X	X	X	X		X				Collect predose (Sections 8.8 and 8.10)
Blood for Genetic Analysis		X								DD			1:				Collect predose from enrolled participants only

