ADA= anti-drug antibodies; AE= adverse event; aPTT= activated partial thromboplastin time; BP= blood pressure; Discon= discontinuation; ECG= electrocardiogram; EQ-5D-5L= Euro quality of life 5-dimensional, 5-level questionnaire; FSH= follicle stimulating hormone; FXI= factor XI; KDQOL-SF= kidney disease quality of life questionnaire-short form; PK= pharmacokinetics; QoL= quality of life; SAE= serious adverse event; WOCBP= women of childbearing potential.

Visit n= Starting from Visit 9 (Day 85) all subsequent visits will be scheduled every 3 months until study completion is reached.

- a. Efficacy Cutoff will be declared when the required number of events has accrued for the primary efficacy endpoint (see Section 9.7). If the study stops at IA, the Final Efficacy Visits will be scheduled to occur within 14 days of Sponsor's notification to stop the study. If the study continues, the Final Efficacy Visits will be scheduled to occur in the 14 days following the Final Analysis efficacy cutoff date.
- b. All WOCBP will have an FSH test at Visit 1. Serum FSH at Visit 2 is only required for participants who have less than 1 year of amenorrhea.
- c. A pregnancy test must be performed at Visit 1. In addition, 1 pregnancy test must be performed within 6 days before the first dose of study intervention (see Section 5.1).
- d. Trough and peak sample collection. Trough sample to be collected pre-dialysis **before any IV heparin is administered to the participant**. Peak sample to be collected approximately 30 minutes **after** infusion ends. If dosing and drawing is from the same access point, flush the access point with saline before sample collection. Record the time samples were drawn, time infusion was started, and time the infusion ended.
- e. Trough sample collection only. To be collected pre-dialysis (before any IV heparin is administered to the participant). Record the time the sample was drawn and the time infusion was started.

Note: For sites participating in the PK substudy, see Table 10 – PK Substudy Schedule of Activities.

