5 STUDY POPULATION

Male/female participants of at least 18 years of age with ESRD receiving hemodialysis via an AVG will be enrolled in this study.

Prospective approval of protocol deviations to recruitment and enrollment criteria, also known as protocol waivers or exemptions, is not permitted.

Inclusion Criteria

5.1

An individual is eligible for inclusion in the study if the individual meets all of the following criteria:

Type of Participant and Disease Characteristics

- 1. Has a current diagnosis of ESRD.
- 2. Has been receiving hemodialysis (including hemodiafiltration) prescribed ≥3 times per week for a minimum of 3 hours per session via mature normally functioning (spKt/V ≥1.2), uninfected AVG. Criterion must be met for at least 75% of the sessions over the 4 weeks prior to randomization.

Demographics

3. Is male or female, ≥18 years of age inclusive, at the time of providing documented informed consent.

Female Participants

- 4. A female participant is eligible to participate if she is not pregnant or breastfeeding, and at least one of the following conditions applies: (Section 10.5.1)
 - Is not a WOCBP

OR

- Is a WOCBP and using an acceptable contraceptive method, or be abstinent from heterosexual intercourse as their preferred and usual lifestyle (abstinent on a long term and persistent basis), as described in Appendix 5 during the intervention period and for at least 90 days, corresponding to the time needed to eliminate any study intervention (eg, 5 terminal half-lives) after the last dose of study intervention. The investigator should evaluate the potential for contraceptive method failure (ie, noncompliance, recently initiated) in relationship to the first dose of study intervention.
- A WOCBP must have a negative highly sensitive pregnancy test (serum) within 6 days before the first dose of study intervention.
- The participant must be excluded from participation if the serum pregnancy result is positive.
- Additional requirements for pregnancy testing during and after study intervention are located in Section 8.3.5.

- The investigator is responsible for review of medical history, menstrual history, and recent sexual activity to decrease the risk for inclusion of a woman with an early undetected pregnancy.
- Contraceptive use by women should be consistent with local regulations regarding the methods of contraception for those participating in clinical studies.

Informed Consent

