8.4.5 Pregnancy and Exposure During Breastfeeding

Although pregnancy and infant exposure during breastfeeding are not considered AEs, any pregnancy or infant exposure during breastfeeding in a participant (spontaneously reported to the investigator or their designee) that occurs during the study are reportable to the Sponsor.

All reported pregnancies must be followed to the completion/termination of the pregnancy.

Any pregnancy complication will be reported as an AE or SAE.

The medical reason (example: maternal health or fetal disease) for an elective termination of a pregnancy will be reported as an AE or SAE. Prenatal testing showing fetus will be born with severe abnormalities/congenital anomalies that leads to an elective termination of a pregnancy will be reported as an SAE for the fetus.

Pregnancy outcomes of ectopic pregnancy, spontaneous abortion, missed abortion, benign hydatidiform mole, blighted ovum, fetal death, intrauterine death, miscarriage, and stillbirth must be reported as serious events (Important Medical Events). If the pregnancy continues to term, the outcome (health of infant) must also be reported.

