8.11.4 Final Efficacy Visit

The Final Efficacy Visit will be conducted for all participants once the planned number of AVG thrombosis events is observed and the efficacy cutoff is declared by the Sponsor.

If applicable, participants will continue in the study until the Final Efficacy Visit but will no longer be administered study intervention at this visit or going forward. Participants who prematurely discontinued study intervention are required to attend the Final Efficacy Visit for collection of clinical events and all assessments and procedures outlined in the SoA.

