8.11.6 Premature Discontinuation Visit

At the Discontinuation Visit, all laboratory testing and procedures outlined in the SoA will be completed. Discontinuation Visit procedures will be performed on participants as soon as possible after discontinuing study intervention (\leq 7 days).

All participants who discontinue study intervention prior to completion of the protocol-specified treatment period will continue to attend all remaining protocol-specified visits, including the Safety Follow-up Visit, which is completed approximately 3 months from the date of last dose of study medication, and perform all procedures stipulated in the SoA. In the

69

PRODUCT: MK-2060

PROTOCOL/AMENDMENT NO.: 007-04

event a participant specifically withdraws consent for further follow-up, no additional information is permitted to be collected.

If the participant does not attend the Discontinuation Visit, a telephone contact for collection of protocol-defined endpoint events should occur. In such cases, the phone contact will not be considered a protocol deviation. If the site is unable to reach the participant, the site will contact the 'external contact person' identified by the participant during screening to collect participant's vital status (Section 8.1.12).

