10.2 Appendix 2: Clinical Laboratory Tests

The tests detailed in Table 9 will be performed by the central laboratory. Local laboratories can be used at Screening.

Protocol-specific requirements for inclusion or exclusion of participants are detailed in Section 5 of the protocol.

Additional tests may be performed at any time during the study as determined necessary by the investigator or required by local regulations.

Table 9 Protocol-required Laboratory Assessments

Laboratory Assessments	Parameters			
Hematology	Platelet count RBC count Hemoglobin Hematocrit	RBC indices: MCV MCH %Reticulocytes	WBC count with differential: Neutrophils Lymphocytes Monocytes Eosinophils Basophils	
Chemistry	Nitrogen (BUN)	AST/ SGOT	Total bilirubin (and direct bilirubin, if total bilirubin is elevated above the ULN)	
	Albumin	Bicarbonate	Chloride	
	Potassium	Sodium	ALT/ SGPT	
	Glucose	Calcium	Alkaline phosphatase	
	Total Protein	Phosphorous		
Other Tests	FSH (as needed for WC)	OCBP)		
	Serum hCG pregnancy test (as needed for WOCBP)			
	Immunogenicity assay (ADA)			
	Coagulation test: INR, PT, aPTT			
	Factor XI activity			
	Serology (HIV antibody, hepatitis B surface antigen, and hepatitis C virus antibody)			

ADA= anti-drug antibodies; ALT= alanine aminotransferase; aPTT= activated partial thromboplastin time; AST= aspartate aminotransferase; BUN= blood urea nitrogen; FSH= follicle stimulating hormone; hCG= human chorionic antigen; HIV= human immunodeficiency virus; MCH= mean corpuscular hemoglobin; MCV= mean corpuscular volume; PT= prothrombin time; RBC= red blood cells; SGOT= serum glutamic-oxaloacetic transaminase; SGPT= serum glutamic-pyruvic transaminase; ULN= upper limit of normal; WBC= white blood cells; WOCBP= women of childbearing potential.

The investigator (or medically qualified designee) must document their review of each laboratory safety report.

Coagulation test results such as PT, INR, and aPTT need to remain blinded to the site and Sponsor staff involved in the study. Laboratory results that could unblind the study will not be reported to investigative sites or other blinded personnel until the study has been unblinded.

10.3 Appendix 3: Adverse Events: Definitions and Procedures for Recording, Evaluating, Follow-up, and Reporting

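### Outside Germany, women of childbearing potential who complete treatment have no scheduled pregnancy test when dosing ends

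*Combined protocol and SAP*

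**What the plan says.** Section 8.3.5.1 leaves the timing of tests to the SoA: WOCBP "will have a serum pregnancy test at visits indicated in the SoA and when pregnancy is suspected". The SoA row "Pregnancy test (Serum) in WOCBP" (Section 1.3) is marked at Visit 1, Visits 7, 8 and 9 (Days 29, 57 and 85), Visit n and the Premature Discontinuation Visit. Footnote c adds only a pre-dose test. The row is blank at both Final Efficacy Visit columns and both Safety Follow-up Visit columns.

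On visit spacing, the SoA notes say: "Starting from Visit 9 (Day 85) all subsequent visits will be scheduled every 3 months until study completion is reached". For completers, dosing ends at the Final Efficacy Visit: Section 8.11.4 says participants "will no longer be administered study intervention at this visit or going forward". For those who stop early, Section 8.11.6 says "Discontinuation Visit procedures will be performed on participants as soon as possible after discontinuing study intervention", with a limit of 7 days.

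Criterion 4 in Section 5.1 requires contraception for at least 90 days after the last dose, and adds: "Additional requirements for pregnancy testing during and after study intervention are located in Section 8.3.5". Appendix 7 requires German sites to test monthly on treatment, at the end of treatment and monthly for 120 days afterwards. Appendix 2 leaves room for unscheduled testing: "Additional tests may be performed at any time during the study as determined necessary by the investigator or required by local regulations".

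**The concern.** Both the Premature Discontinuation Visit and the treatment-period Final Efficacy Visit mark the end of dosing. A woman who stops early has a scheduled test at that point; a woman who completes does not. Section 5.1 sends the reader to Section 8.3.5 for testing after treatment, but for completers outside Germany that section adds only testing on suspicion.

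Weekly dosing continues after the last 3-monthly test, so the schedule does not establish a completer's pregnancy status at the end of exposure. Detection then depends on suspicion, investigator judgement, local rules or a report at adverse event review. This matters because Section 8.4.5 says "All reported pregnancies must be followed to the completion/termination of the pregnancy": a pregnancy conceived on treatment that is never recognised or reported is not followed to outcome. Section 2.2.2 gives a half-life of about 19 days after multiple dosing in this population, so exposure also continues past the last dose.

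**Working it through.** The plan states no figure on this point. The check is a reading of the SoA followed by simple arithmetic.

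**1. The SoA row.** The table has 16 visit columns and a notes column. Counted from the left, the pregnancy row is marked in columns 1, 7, 8, 9, 10 (Visit n) and 13 (Premature Discontinuation Visit). Column 11, the treatment-period Final Efficacy Visit, is blank. The note on Germany falls in the notes column, so the row aligns from both ends and the blank does not look like an extraction shift.

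**2. Comparison with the other rows.** Sixteen items are marked at the Premature Discontinuation Visit: medication review, full physical examination, weight, vital signs, ECG, clinical events, vital status, AE/SAE review, questionnaires, pregnancy test, hematology, liver function, chemistry, PK, ADA and PT/aPTT/FXI activity. Fifteen of them are also marked at the treatment-period Final Efficacy Visit. The missing one is the pregnancy test.

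**3. Gap between last test and Final Efficacy Visit.** The Final Efficacy Visit follows the event-driven cutoff, not the 3-month cycle. With visits about 91 days apart, the gap runs from 0 to about 91 days, with mean 91 / 2 = 45.5 days if the cutoff falls uniformly within the cycle.

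**4. Doses given within the gap.** Take the last test as day 0, weekly dosing, and no dose at the Final Efficacy Visit.
- Gap of 91 days: doses on days 7 to 84, so 84 / 7 = 12 after the test day (13 if a dose on the test day is counted).
- Visit n held 7 days early, gap of 98 days: doses on days 7 to 91, so 91 / 7 = 13 after the test day.
- Next Visit n also allowed to run 7 days late: 91 + 7 + 7 = 105 days; doses on days 7 to 98, so 98 / 7 = 14 after the test day.

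**5. Expected pregnancies in the gap.** The documents give neither the WOCBP share nor a conception rate. Assumed ranges are 2% to 10% of the 489 participants and 1% to 5% conceptions per woman-year.

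Expected number = 489 × share × rate × 45.5 / 365.25

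| Share of WOCBP | Women | Conceptions per year | Expected pregnancies |
|---|---|---|---|
| 2% | 9.8 | 1% | 0.012 |
| 10% | 48.9 | 5% | 0.305 |

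These figures are upper-side for each assumption pair, because early discontinuers and German participants have not been removed.

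**6. After the fix.** With the mark added, all 16 of the 16 items would be scheduled at both end-of-dosing visits.

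**The case against.** The strongest reply is that nothing in the protocol promises completers an end-of-treatment test, so the plan does not contradict itself. The asymmetry could also be deliberate. A positive test leads to stopping study treatment (Sections 7.1 and 8.3.5.1), and at the Final Efficacy Visit dosing is already over. Early discontinuers differ, because Section 7.1 allows some to restart. This rationale is plausible but appears nowhere in the documents, and it leaves out the other purpose of testing, which is to find pregnancies that must be followed to outcome.

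A second reply is that Final Efficacy Visit columns need not mirror the Premature Discontinuation Visit: in the separate Final Efficacy Visit column for early discontinuers, 5 of the same 16 items are blank. That is correct, but those participants were already tested when dosing stopped. Completers were not.

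Third, other safeguards exist. Contraception is required, AE review takes place at the Final Efficacy Visit and again about 90 days later, and all pregnancies in that period are reportable. A conception goes unfollowed only if it stays unsuspected and unreported through that further contact. This stands: the number of pregnancies that only the added test would find is smaller than the 0.01 to 0.3 conceptions counted above.

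Finally, a test at the Final Efficacy Visit cannot undo exposure and does not cover the 90-day contraception period that follows. This also stands, and limits what the fix achieves.

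**Conclusion.** The concern holds. Outside Germany, no scheduled test establishes whether a completing WOCBP is pregnant when dosing ends, although early discontinuers are tested at the equivalent point. The gap since the last scheduled test is up to about 91 days with 12 later doses, or somewhat longer if visit windows are used. About 0.01 to 0.3 pregnancies are expected to fall in it across the trial, on assumed shares and conception rates that the documents do not supply. Few participants are affected, and the efficacy analysis, power and error control are untouched. This is a minor gap in safety follow-up, worth closing because closing it costs almost nothing.

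**What to change.** In the SoA pregnancy-test row, add a mark at the treatment-period Final Efficacy Visit. In Section 8.3.5.1, add a sentence stating that WOCBP have a serum pregnancy test when study intervention ends, at the Final Efficacy Visit or the Premature Discontinuation Visit as applicable. Appendix 7 can stay as it is.

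The cost is one serum hCG assay per completing WOCBP: at most about 10 to 49 assays under the assumed 2% to 10% share. No extra draw is needed, because blood for hematology, liver function, chemistry, PK, ADA and PT/aPTT/FXI activity is already taken at that visit. Sample size and analysis do not change.

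Optionally, add a test at the Safety Follow-up Visits to cover the end of the 90-day contraception period. That would need one additional draw, since no laboratory samples are scheduled there.
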